#### 7.3 Serious Adverse Events

An SAE is any untoward medical occurrence that:

- Results in death.
- Is life-threatening. NOTE: The term 'life threatening' in the definition of "serious" refers to an event in which the subject was at risk of death at the time of the event; it does not refer to an event which hypothetically might have caused death if it was more severe.
- Results in persistent or significant disability/incapacity.
- Requires in subject hospitalization or prolongation of existing hospitalization. NOTE: Hospitalizations, which are the result of elective or previously scheduled surgery for pre-existing conditions, which have not worsened after entry into the study, should not be classified as SAEs. For example, admission for a previously scheduled ventral hernia repair would not be classified as an SAE; however, complication(s) resulting from a hospitalization for an elective or previously scheduled surgery that meet(s) serious criteria must be reported as SAE(s).
- Is a congenital anomaly/birth defect.
- Is an important medical event.

NOTE: Medical or scientific judgment should be exercised in deciding whether reporting is appropriate in other situations, such as important medical events that may not be immediately life threatening or result in death or hospitalization but may jeopardize the subject or may require medical or surgical intervention to prevent one of the other outcomes listed in the above definition. These should also be considered serious. Examples of such events are invasive or malignant cancers, intensive treatment in an emergency room or at home for allergic bronchospasm, blood dyscrasias, or convulsions that do not result in hospitalization, or development of drug dependency or drug abuse.

All SAEs will be collected from the time of informed consent until 30 days after the last study treatment regardless of study drug relationship, and must be reported to Nabriva Therapeutics AG or their representative (Covance Pharmacovigilance & Drug Safety Services [PV & DSS]) within 24 hours of knowledge of the event (this refers to any AE that meets one or more of the aforementioned serious criteria).

The sponsor will not routinely unblind the therapy assignment for an individual subject in the event of a serious adverse event. However, unblinding of an individual subject may occur if this information is requested by the Investigator, if the Sponsor determines that the information is necessary to adequately assess safety, or if this information is required for reporting to local regulatory authorities (see Section 5.6).

All serious adverse events and suspected unexpected serious adverse events (SUSARs) will be reported by the sponsor to the relevant competent authorities in accordance with the European Directive 2001/20/EC, as applicable.

#### 7.4 Symptoms of the Disease Under Study

In this study, clinical signs and symptoms of pneumonia which are assessed daily per protocol (i.e., dyspnea, cough, sputum production, and chest pain) will not be reported as adverse events unless they meet the definition of a serious adverse event.

#### 7.5 Other Reportable Events

Certain events that occur should be reported to the Sponsor as Other Reportable Events. These include the following:

- Potential Hy's Law (PHL)
  - The investigator is responsible for prompt reporting of any patients who has had both (1) AST or ALT > 3 x ULN and (2) total bilirubin > 2 x ULN at any point in the study (i.e., meets criteria for Potential Hy's Law). The investigator must complete the Hy's Law eCRF. Liver laboratory results should be followed locally every several days until resolution or stabilization of the laboratory abnormalities and reported using an unscheduled laboratory eCRF. If subsequent to the initial report of PHL, the investigator determines that the case meets serious criteria, it should be reported as an SAE using standard reporting procedures.
- Pregnancy exposure (subject becomes pregnant while taking study drug)
  - Subjects who are pregnant at Screening are not permitted to take part in this study, however, Nabriva Therapeutics AG or their representative must be notified of any subjects that become pregnant while participating in this study (or the partner of a male subject). Although pregnancy is not technically an AE, all pregnancies must be followed to conclusion to determine their outcome. This information is important for both drug safety and public health concerns. It is the responsibility of the Investigator or designee to report any pregnancy in a subject that occurs during this study to Nabriva Therapeutics AG or their representative.
- Lactation exposure (subject was taking study drug while nursing an infant)
- Accidental exposure (someone other than the study subject was exposed to study drug)
- Overdose (subject received more than the prescribed dose of study drug within a given timeframe)
- Other medication errors that potentially place subjects at a greater risk of harm than was previously known or recognized (e.g., study drug was administered by an incorrect route).

#### 8 DRUG SUPPLIES

#### 8.1 Lefamulin (BC-3781)

The active substance being investigated in this study is lefamulin (BC-3781), present in the drug product as the acetate salt (BC-3781.Ac). Physicochemical properties can be found in the Lefamulin Investigator's Brochure.

Oral lefamulin is supplied by the Sponsor as 600 mg yellow oval film coated immediaterelease tablets. Details of the composition are provided in the Lefamulin Investigator's Brochure.

#### 8.2 Moxifloxacin

The oral dose of moxifloxacin is provided by the Sponsor as an over-encapsulated film coated tablet containing 400 mg as hydrochloride.

Additional details regarding moxifloxacin are found in the product monograph.

#### 8.3 Placebo

The following oral placebo tablets will be supplied by the Sponsor: lefamulin placebo tablet and moxifloxacin placebo capsule.

Further details may be found in the Study Pharmacy Manual.

#### 8.3.1 Packaging and Labeling

Study drugs will be packaged and labeled in accordance with the applicable regulatory authority requirements.

#### 8.3.2 Storage of Study Drugs

Access to all study drugs at the site must be restricted to designated study personnel throughout the study.

Oral study medication will be supplied in blister packs. Two different blister packs will be provided:

- Lefamulin tablets and moxifloxacin placebo capsules.
- Over-encapsulated moxifloxacin tablets and lefamulin placebo tablets

The two blister packs must be stored at controlled room temperature (15 to 25 °C).

#### 8.3.3 Product Accountability

The Investigator is responsible for study medication accountability, reconciliation, and record maintenance. In accordance with all applicable regulatory requirements, the Investigator or

designated study personnel must maintain study drug accountability records throughout the course of the study. This person(s) will document the amount of study drug received from the supplier, the amounts dispensed to subjects as well as lot numbers and expiration / retest date of study medications.

At the conclusion of the study, any unused study drug will be returned to either a Sponsor-designated recipient or destroyed at the site after discussion with the Sponsor. If no supplies remain, this will be recorded in the drug accountability section of the final monitoring report.

#### 9 STATISTICAL ANALYSIS

Inferential statistical analyses of the primary and secondary outcomes will be conducted as outlined below. Descriptive statistics, including the numbers and percentages for categorical variables, and the numbers, means, standard deviations, medians, minimums, and maximums for continuous variables will be provided. Additional statistical analyses, other than those described in this section, may be performed if deemed appropriate. A description of the statistical analysis performed on the study data will be outlined in the SAP.

As a consequence of differing regulatory requirements for the choice of primary efficacy analysis variable and statistical analyses of this study, 2 separate regional comprehensive SAPs will be prepared (FDA and EMA) and finalized before database lock and analysis of the data.

Exploratory evaluation of a variety of health utilization variables (e.g., length of hospital stay, duration of antibiotic therapy, discharge status, discharge destination) as well as a PRO instrument will be performed. Details for this exploratory analysis will be presented in a separate SAP and results will be presented in a stand-alone clinical study report.

# 9.1 Treatment Comparison of Interest

All comparisons will be for lefamulin versus comparator therapy (moxifloxacin).

# 9.2 Sample Size Determination

A total of 738 subjects will be randomized in a ratio of 1:1 (lefamulin:moxifloxacin) resulting in 369 subjects in the lefamulin arm and 369 in the moxifloxacin arm in this study. The total number of subjects included in this study is sufficient to achieve the primary and secondary study objectives based on statistical considerations.

Retrospective analyses of clinical study data for patients with CABP of varying severity as well as 2 recent clinical trials in CABP indicate the point estimates for an ECR responder at Days 3-5 range from 72% to 81% (FDA, 2011; Barrera et al., 2016; Cempra, 2015; Oldach et al., 2015). Thus, it is reasonable to assume that in a prospective study of subjects with CABP, the proportion of subjects who are responders for ECR at  $96 \pm 24$  hours post first dose of study drug will be approximately 79%.

The primary efficacy analysis variables used for NI analyses for the Marketing Authorization Application (MAA) to the EMA will be the proportion of subjects with an IACR of Success at TOC in the mITT and CE-TOC Analysis Sets. In recent clinical studies, IACR success rates at the TOC Visit in the CE Analysis Set ranged from 77% to 93% (Cempra, 2015) and in the ITT Analysis Set ranged from 85% to 89% depending on the antibiotics under study and the severity of the CABP. Based on these data, an 85% IACR success rate in the CE-TOC Analysis Set was chosen for determination of the sample size. The success rate is expected to be about 5% lower in the mITT Analysis set. It is expected that <1% of subjects will be excluded from the mITT Analysis Set and thus, the sample size determination assumes the same number of subjects in the ITT and mITT Analysis Sets.

Utilizing an anticipated ECR responder rate of 79% in the ITT Analysis Set, a 1:1 randomization ratio, a two-sided alpha of 0.025, and a continuity corrected Z-test with unpooled variance, a sample size of 738 subjects (369 subjects in the lefamulin group and 369 in the moxifloxacin group) provides 90% power to establish the NI of lefamulin to moxifloxacin for ECR using a NI margin of 10.0% at the ECA. Assuming an IACR success of 80% and 85% in the mITT and CE-TOC Analysis Sets, respectively, and a clinical evaluability rate of 80%, there is 91% power for demonstration of NI for IACR at the TOC Visit using a 10% NI margin.

The calculated power in each analysis set for the primary and secondary outcomes is provided in Table 6 below.

Table 6. Power Calculations for the Primary and Secondary Efficacy
Outcomes

	Primary Outcome (FDA) (ECR 96 ± 24 hours After the First Dose of Study Drug)	(Investigator's Assessmen	Outcome nt of Clinical Response at ry for EMA)
Analysis Set	ITT	mITT	CE-TOC
NI Margin	10%	10%	10%
N	738 (369:369)	738	590
Outcome Rate	79%	80%	85%
Evaluability Rate	NA	NA	80%
Power	90%	91 %	91%

CE = clinically evaluable; ITT = intent to treat; mITT = modified ITT; TOC = test of cure

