#### **Statistical Methods:**

A 2-sided unstratified 95 % confidence interval (CI) for the observed difference between treatment groups (lefamulin minus moxifloxacin) in ECR responder rates at  $96 \pm 24$  hours post first dose will be calculated using a continuity corrected Z-statistic. Non-inferiority for the primary efficacy analysis variable (FDA) will be concluded if the lower limit of the 2-sided 95% CI is greater than -10.0% in the ITT Analysis Set.

For the efficacy outcome measure of IACR of Success at TOC in the mITT and CE-TOC Analysis Sets, unstratified 95% CIs will be calculated using a continuity corrected Z-statistic (FDA secondary efficacy outcome). For the primary analysis for the EMA, a stratified (for the randomization stratification factors) 2-sided 95% CIs will be calculated using the method of Miettinen and Nurminen. Non-inferiority for the primary efficacy analysis variable (EMA) will be concluded if the lower limit of the 2-sided stratified 95% CI is greater than -10% for both the mITT and CE-TOC Analysis Sets.

The number and percentage of subjects with an ECR of Responder at  $96 \pm 24$  hours will also be presented for the microITT Analysis Set, and a 2-sided unstratified 95% CI for the difference in responder rate will be calculated using a continuity-corrected Z-statistic. However, the formal test of NI will be conducted in the weighted (based on the inverse variance of each effect size) pooled population from this study and a second study in CABP.

The incidence of treatment-emergent AEs (TEAEs), serious AEs (SAEs), deaths, and discontinuations of study drug due to an AE or SAE will be summarized by System Organ Class (SOC) and Preferred Term according to the Medical Dictionary for Regulatory Activities (MedDRA), by relationship to study drug, and by severity. The incidence of potentially clinically significant laboratory results, vital signs, and ECGs will be summarized.

Nabriva Therapeutics AG Clinical Protocol NAB-BC-3781-3102

Table 1. Schedule of Assessments and Procedures

Agreement on Busselines	Screening/	Study Drug Administration			$EOT^d$	Follow-up Visits		
Assessment or Procedure	Baseline a	Day 1 b	Day 2	Day 3	Days 4 to 7 c	Visit	TOC e	$LFU^f$
Informed consent form completed g	X							
Verify inclusion/exclusion criteria	X							
Medical and surgical history	X							
Determine PORT Risk Class	X							
Height and weight	X							
Randomization	X							

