Additional analyses of the primary efficacy outcome will be conducted. ECR will be assessed separately across the geographic regions, prior antibiotic use, and PORT risk class strata. For each geographic region, prior antibiotic use, and PORT risk class stratum, a 2-sided 95% CI for the observed difference in ECR responder rates will be calculated for the ITT Analysis Set. Sensitivity analyses of ECR include determination of a stratified 95% CI (adjusted for the randomization stratification factors) and considering all subjects with missing data (i.e., Indeterminates) at  $96 \pm 24$  hours after the first dose of study drug as responders for ECR (these subjects are considered non-responders in the primary analysis). For the second sensitivity analysis, an unstratified 95% CI will be computed for the difference in the responder rates between lefamulin and moxifloxacin. Subgroup analyses of the primary efficacy outcome will also be conducted for descriptive purposes and will be detailed in the SAP. For both ECR and IACR, additional analyses will be conducted whereby failures will be reclassified as Indeterminate if they received less than 48 hours of study medication.

For the EMA primary analysis (secondary analysis for the FDA), the number and percentage of subjects in each treatment group with an IACR of Success, Failure and Indeterminate (by definition Indeterminates are not included in the CE-TOC Analysis Set) at TOC will be reported in the mITT and CE-TOC Analysis. Subjects who have an IACR of Failure at EOT will be considered to have an IACR of Failure at TOC. The primary analysis for the EMA will utilize 2-sided stratified (for the randomization stratification factors) 95% CIs calculated using the method of Miettinen-Nurminen. If the lower limit of the 95% CI for the difference in success rates in both the mITT and CE-TOC Analysis Sets is greater than -10%, the NI of lefamulin to moxifloxacin will be concluded. Two-sided unstratified 95% CIs will be calculated for the difference in success rates at TOC in the mITT and CE-TOC Analysis Sets (FDA secondary outcome).

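### The 91% power for IACR at TOC holds in each analysis set separately; the EMA rule requires both sets, and the power for that is about 87% (about 89% with the planned Miettinen-Nurminen interval)

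*Protocol*

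**What the plan says.** Protocol Section 9.2 sizes the trial at 738 subjects, 369 per arm. For the EMA outcome it gives its inputs as follows: "Assuming an IACR success of 80% and 85% in the mITT and CE-TOC Analysis Sets, respectively, and a clinical evaluability rate of 80"%. It then concludes that "there is 91% power for demonstration of NI for IACR at the TOC Visit using a 10% NI margin". The Synopsis (Statistical Considerations) and SAP Section 7.1 repeat that sentence. Protocol Table 6 and SAP Table 7 show 91% for mITT (N = 738) and 91% for CE-TOC (N = 590) in separate columns, and the text introduces these tables as power by analysis set.

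The EMA decision rule is in Protocol Section 9.6.1. If the lower limit of the 95% CI for the difference "in both the mITT and CE-TOC Analysis Sets is greater than -10%, the NI of lefamulin to moxifloxacin will be concluded". The Synopsis (Statistical Methods) has the same condition: the limit must be "greater than -10% for both the mITT and CE-TOC Analysis Sets". The interval for this analysis is a stratified Miettinen-Nurminen interval.

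**The concern.** The sentence gives one power for showing non-inferiority on the endpoint, but the rule has two conditions that must both be met. A power computed for one condition is the power of the rule only if the two conditions always succeed or fail together. They do not: about 20% of mITT subjects are outside CE-TOC, and their outcomes move one estimate and not the other.

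At stake is the stated chance of meeting one of the protocol's two primary objectives. As written, the EMA objective (91%) looks slightly better powered than the FDA objective (90%). Once both sets are required, it is slightly less well powered.

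**Working it through.** **Inputs (Protocol Section 9.2 and Table 6)**
- Arm size: 369. mITT is taken as equal to ITT: "the sample size determination assumes the same number of subjects in the ITT and mITT Analysis Sets".
- CE-TOC: 590 subjects, 295 per arm (80% of 738 is 590.4).
- IACR success: 80% in mITT and 85% in CE-TOC, in both arms (no true difference). Margin: 0.10.
- Test: the Section 9.2 description for ECR is "a two-sided alpha of 0.025, and a continuity corrected Z-test with unpooled variance". SAP Section 7.1 calls the same alpha one-sided. Only the one-sided reading reproduces the printed powers. With a two-sided 0.025, ECR would be 84.2%, mITT 85.6% and CE-TOC 85.2%. One-sided 0.025 is used below.

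**Step 1: reproduce the printed figures**

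Power = Φ[(0.10 − 1/n) / √(2p(1−p)/n) − 1.96], where 1/n is the continuity correction for equal arms.
- mITT: p = 0.80, n = 369, SE = 0.0294. Φ(1.344) = 91.0%.
- CE-TOC: p = 0.85, n = 295, SE = 0.0294. Φ(1.326) = 90.8%.
- ECR, as a check: p = 0.79, n = 369 gives 90.1%, against the printed 90%.

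The 91% is therefore the power in one set at a time.

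**Step 2: correlation of the two estimates**

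CE-TOC is a subset of ITT and requires a minimum amount of study drug, so it lies within mITT. The mITT difference is then 0.8 times the CE-TOC difference plus 0.2 times the difference in the remaining subjects. The plan's rates imply a success rate in those remaining subjects of (0.80 − 0.80 × 0.85)/0.20 = 60%.

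The covariance of the two differences is (295/369) × Var(CE-TOC difference), so

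ρ = √(0.1275/0.16) × √(295/369) = 0.893 × 0.894 = 0.798.

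**Step 3: probability of passing both**

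The bivariate normal probability with limits 1.344 and 1.326 and ρ = 0.798 is 86.8%. One million simulated trials were used as a check, first with evaluability random at 80% and then with exactly 295 evaluable per arm:

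| Method | mITT | CE-TOC | Both |
|---|---|---|---|
| Continuity-corrected Z, random evaluability | 91.0% | 90.7% | 86.8% |
| Continuity-corrected Z, 295 fixed | 91.7% | 90.8% | 87.5% |
| Miettinen-Nurminen unstratified, random evaluability | 92.3% | 92.1% | 88.6% |
| Miettinen-Nurminen unstratified, 295 fixed | 93.0% | 92.2% | 89.3% |

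Stratified Miettinen-Nurminen (eight strata, Cochran-Mantel-Haenszel weights, 100,000 trials per scenario) gave 88.6% to 88.7% for both sets. The documents do not give stratum shares. I assumed US 10% to 50%, prior antibiotic 20% to 25% and PORT III/IV 50%, with equal success rates across strata. The result did not depend on these choices.

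**Step 4: sensitivity to the correlation**

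| ρ | Z, corrected | Z, uncorrected |
|---|---|---|
| 0 | 82.6% | 85.5% |
| 0.7 | 86.0% | 88.2% |
| 0.8 | 86.8% | 89.0% |
| 0.9 | 88.0% | 90.0% |
| 1 | 90.8% | 92.4% |

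The right-hand column is an uncorrected Z, which only approximates Miettinen-Nurminen. With the sizing test, the joint power rounds to 91% only when the correlation is essentially 1.

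**The case against.** The strongest reply is that no printed number is wrong. The quoted sentence lists its assumptions set by set, the next sentence in Section 9.2 says the power is given for each analysis set, and Table 6 has separate columns. Read together, these make the per-set meaning recoverable. That is true of Section 9.2, but the label does not turn the sentence into a statement about the EMA rule. The Synopsis carries the sentence with no table and no per-set label.

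A second objection is that 87% comes from a test the EMA conclusion will not use. This stands in part. The 87% is the like-for-like comparison with the printed 91%, because both use the sizing test. With the planned method the shortfall is only about 2 points, so both figures should be given.

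Third, the gap is small beside the uncertainty in the assumed rates. Section 9.2 cites CE success from 77% to 93%, over which CE-TOC power alone runs from 80% to 99.6%. Raising both assumed rates by 2 points (82% and 87%) brings the joint power with the sizing test to 90%. This bears on how much weight the point carries. It does not make 91% the right figure under the stated assumptions.

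Fourth, this SAP covers the FDA analyses, and the EMA analyses go to an addendum that is not available here and might give a joint power. But SAP Section 7.1 and Table 7 already print the IACR power and label it as primary for the EMA, so the clarification belongs there too.

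**Conclusion.** The concern holds. The 91% is right for each set and overstated for the EMA conclusion that needs both. Under the plan's inputs the joint power is 86.8% with the sizing test (87.1% to 87.5% if 295 evaluable per arm is treated as fixed) and 88.6% to 89.3% with Miettinen-Nurminen. The shortfall is about 4 points and about 2 points respectively.

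This rests on no true difference between arms, evaluability of 80% regardless of arm, CE-TOC lying within mITT, and a one-sided 0.025 level. Joint power stays well above 80% under these assumptions, so this is a correction to a reported figure. It is no evidence that the trial is too small.

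**What to change.** In Protocol Section 9.2, the Synopsis and SAP Section 7.1, replace the single power statement with wording such as: 91% power in each analysis set; about 87% power (about 89% with the Miettinen-Nurminen interval) to meet the -10% criterion in both mITT and CE-TOC, as the EMA conclusion requires. Add a column for both sets to Protocol Table 6 and SAP Table 7, and state the assumptions behind it (80% evaluable, 60% success outside CE-TOC, correlation about 0.80). If the EMA addendum gives a power, it should match.

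The cost is wording only, with a slightly less favourable figure. The sample size, margin, decision rule and analyses stay as they are. For scale, 90% joint power would need about 808 subjects with the continuity-corrected test, or about 762 with an uncorrected Z as a rough stand-in for Miettinen-Nurminen. I do not recommend that change.
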